**Figure 1 Overall Study Design**

EOT: End of Treatment

### **9.1.1 Screening Period**

The purpose of the Screening Period is to obtain informed consent and to establish protocol eligibility. Informed consent will be obtained after the study has been fully explained to each subject and before the conduct of any screening procedures or assessments. Procedures to be followed when obtaining informed consent are detailed in Section 5.3.

Subjects must have a diagnosis of Parkinson's Disease and receive levodopa at a stable dose for at least 4 weeks prior to the screening visit. After signed informed consent is obtained from the subject or for subjects from Legally Acceptable Representatives (LARs), a medical history interview, identification of prior and concomitant medications, identification of concomitant therapies, height, weight, physical examination, urine pregnancy test (females of childbearing potential only), 12-lead electrocardiogram (ECG; if deemed necessary by an investigator), vital signs, clinical laboratory tests (hematology, chemistry, and urinalysis), and Adverse Events (AE) assessment will be conducted for evaluation of eligibility criteria, and will include confirmation that the subject meets diagnostic criteria for Parkinson's Disease.

At Visit 1 (Screening), subjects will perform the Mini-Mental State Examination (MMSE) among the efficacy assessments. Also, a diary will be handed out to subjects and/or their caregivers, and investigator will train them how to complete the diary. Subjects who meet the eligibility criteria of the study will be instructed to complete the diary for 3 consecutive days prior to Visit 2 (Baseline).

If subjects have previously taken medication such as COMT inhibitor and/or MAO-B inhibitor, they have to undergo an appropriate wash-out period for each medication (3 days for COMT inhibitor; 14 days for MAO-B inhibitor).

### **9.1.2 Baseline Period**

At Visit 2 (Baseline), subjects will return to the site after they complete the diary for at least 3 consecutive days. At Visit 2 (Baseline), safety assessments including AE assessment, vital signs, weight (if deemed necessary by an investigator), and physical examination will be conducted.

Efficacy assessments including Parkinson's Disease Questionnaire-39 (PDQ-39), Movement Disorder Society - Unified Parkinson's Disease Rating Scale (MDS-UPDRS) Part 3 and Part 4, and King's Parkinson's disease Pain Scale (KPPS) will be conducted. The investigators will also review the completed subject diary with subjects.

The study drug will be distributed to subjects who meet the eligibility criteria at Visit 2 (Baseline). The subjects will be instructed to take the study drug every day starting from the next day after Visit 2 (Baseline).

### 9.1.3 Treatment Period

Subjects whose screening assessments including the wash-out period and evaluations are completed and reviewed by the investigators and who continue to meet all of the inclusion/exclusion criteria will enter the Treatment Period. Subjects will take the study drug every day for 18 weeks.

The dose of the study drug is 50 mg once a day for 2 weeks (14 days) starting from the next day after Visit 2 (Baseline), and 100 mg once a day afterwards. Subjects who need to increase the dose at the discretion of an investigator shall visit the site (unscheduled) prior to the dose increase.

Subjects whose dose cannot be increased to 100 mg/day within 4 weeks following Visit 2 (Baseline) will be dropped out from the clinical trial.

If Adverse Events (AE) occur in subjects who have increased the dose, the dose may be reduced back to 50 mg/day at the discretion of an investigator through unscheduled site visit or phone visit. After reduction from 100mg/day to 50mg/day, the dose may be increased back to 100 mg/day at the discretion of an investigator.

Subjects will return to the site at 8 weeks and 18 weeks for Visit 3 and Visit 4 (EOT), respectively. The “windows” permitted for Visit 3 (8 weeks) will be -4 weeks and +2 weeks; for Visit 4 (18 weeks: EOT) will be +/- 2 weeks. Safety assessments including AE assessment, 12-lead ECG (if deemed necessary by an investigator), vital signs, weight, physical examination, clinical laboratory tests (hematology, chemistry, and urinalysis), and urine pregnancy test (females of childbearing potential only) will be conducted according to the schedule for each visit during Treatment Period. Efficacy assessments including PDQ-39, MDS-UPDRS Part 3 and Part 4, KPPS, and MMSE will be conducted at Visit 4 (EOT). Subjects will complete the diary for at least 3 consecutive days prior to Visit 4 (EOT), and the investigators will review the completed diary together with subjects at Visit 4 (EOT).

### 9.1.4 Taper Period

Of the subjects who have completed 18 weeks of treatment, those who require tapering will enter a Taper Period for 1 week. After the completion of the Taper Period, subjects will return to the site for Visit 5. At Visit 5, safety assessments including AE assessment, vital signs, weight (if deemed necessary by an investigator), and physical examination will be conducted. For those subjects participating in the Taper Period, their participation in the study will be completed after the completion of Visit 5.

The Taper Period may be omitted if the subject’s daily dose of the study drug at the end of treatment is 50mg, if subjects will continue to take the study drug after the completion of the trial, or if it is considered not required by an investigator. For the subjects who do not require the Taper Period, their participation in the study will be completed after the completion of Visit 4 (EOT).

## 9.2 Discussion of Study Design

This study is a multi-center, open-label, single-arm, interventional study to evaluate the efficacy and safety of the study drug as add-on therapy to levodopa in subjects with Parkinson's Disease according to standard clinical practice. The study drug has dopaminergic and non-dopaminergic pathways so it improves motor symptoms as well as non-motor symptoms. For this reason, this study will evaluate the "off" time and PDQ-39 as co-primary endpoints.

## 9.3 Selection of Study Population

Approximately 199 subjects will be enrolled at approximately 20 sites in South Korea. Subjects who do not meet all of the inclusion criteria or who meet any of the exclusion criteria will not be eligible to participate in this study.

### 9.3.1 Inclusion Criteria

To be eligible for inclusion into this trial, the subjects must fulfill all of the following criteria:

1. Male or female, age  $\geq 19$  years at the time of informed consent
2. Patients who meet the clinical diagnostic criteria of Movement Disorder Society (MDS) diagnostic criteria 2015 for Parkinson's disease, have motor fluctuations with  $\geq 1.5$  hours of "off" time throughout the day which is confirmed at the time of Screening and take levodopa 3 or more times a day
3. Parkinson's Disease patients who are receiving levodopa without COMT inhibitor and/or MAO-B inhibitor

CCI

4. Be able to maintain an accurate and complete diary with the help of a caregiver as needed, recording "on" time, "on" time with dyskinesia, "off" time, and time asleep
5. Be able to provide written informed consent
6. Patients whose cognitive function, at the discretion of an investigator, is at a level appropriate to participate in the clinical trial (i.e., with a GDS score of 3 or less or a CDR of 0.5 or less within 3 months prior to Screening)

### 9.3.2 Exclusion Criteria

To be eligible for inclusion into this trial, the subjects must not meet any of the following criteria:

1. Females who are planning for pregnancy, pregnant or breastfeeding
2. Prior use of safinamide
3. If patients have previously taken medication such as COMT inhibitor and/or MAO-B inhibitor, they have to take appropriate wash-out period for each medication.(3 days for COMT inhibitor; 14 days for MAO-B inhibitor)
4. Use of medications for depression or psychosis within 5 weeks prior to Screening Visit
5. History of allergic response to levodopa, or other anti-Parkinsonian agent
6. Hypersensitivity or contraindications to MAO-B inhibitors
7. Confirmed ophthalmologic history including any of the following conditions: albino subjects, family history of hereditary retinal disease, progressive and/or severe diminution of visual acuity (i.e., 20/70 on Snellen Chart), retinitis pigmentosa, retinal pigmentation due to any cause, any active retinopathy or ocular inflammation (uveitis), or diabetic retinopathy.
8. Patients who did not consent to having at least 7 days of washout period prior to Visit 2, if known to take narcotic analgesics 7 days prior to Screening Visit (eg, pethidine hydrochloride-containing products, tramadol hydrochloride, or tapentadol hydrochloride)
9. History of serotonergic medications administration (eg, tricyclic antidepressants, tetracyclic antidepressants, selective serotonin reuptake inhibitors, serotonin–noradrenaline reuptake inhibitors, selective noradrenaline reuptake inhibitor, or noradrenergic and serotonergic antidepressant) within 5 weeks prior to the Screening Visit
10. Administering central nervous system stimulants (eg, methylphenidate hydrochloride, lisdexamfetamine mesilate)
11. Administering dextromethorphan
12. Patients with clinically significant liver function abnormalities defined as > 1.5 times of the upper limit of the normal range of total bilirubin or > 3 times of the upper limit of the normal range of ALT or AST; re-examination and re-screening are allowed once within the screening period
13. Have a history of hypersensitivity to any of the ingredients of the product
14. Currently enrolled in another clinical trial or used any investigational drug/biologics or device within 30 days or 5 × the half-life, whichever is longer, preceding informed consent

### 9.3.3 Removal of Subjects from Therapy or Assessment

The investigators may withdraw the subjects from the study at any time for safety or administrative reasons and noncompliance with study procedures (e.g., omission of efficacy evaluation, omission of subject diary completion, use of prohibited medication or therapy, deviation from the dose limitation of concomitant medication, deviation from the dose increase

schedule of study drug, etc.) Also, subjects whose dose of study drug cannot be increased to 100 mg/day within 4 weeks of Visit 2 (Screening) will be withdrawn from the study. Subjects may stop the study drug administration or withdraw from the study at any time for any reason.

Subjects who prematurely discontinue the administration of the study drug should visit the site as soon as practicable (preferably within 7 days) to complete the Premature Discontinuation Visit.

## 9.4 Treatment

### 9.4.1 Treatment Administered

Subjects who are enrolled in this study will be treated with the study drug for approximately 18 weeks. The dose and administration of the study drug is as follow:

The dose of the study drug is 50 mg once a day for 2 weeks (14 days) starting from the next day after Visit 2 (Baseline), and 100 mg once a day afterwards. Subjects who need to increase the dose at the discretion of an investigator shall visit the site (unscheduled) prior to the dose increase.

If Adverse Events (AE) occur in subjects who have increased the dose, the dose may be reduced back to 50 mg/day at the discretion of an investigator through unscheduled site visit or phone visit. After reduction from 100mg/day to 50mg/day, the dose may be increased back to 100 mg/day at the discretion of an investigator.

If, following the dose increase to 100mg/day, moderate or severe hepatic impairment occurs according to Child-Pugh classification, study drug should be administered as per below guideline.

- Moderate hepatic impairment (Child-Pugh B): Do not exceed 50 mg once daily
- Severe hepatic impairment (Child-Pugh C): Contraindicated (Termination of study drug required)

[Child-Pugh Classification]

Parameter	Abnormal value or degree	Grade Score
Encephalopathy*	None 1 and 2 3 and 4	1 2 3
Ascites	None Mild Moderate	1 2 3
Total bilirubin (mg/dL)	< 2 2 - 3 > 3	1 2 3

Albumin (g/dL)	> 3.5	1
	2.8 - 3.5	2
	< 2.8	3
Prothrombin Time (seconds)	< 4	1
	4 - 6	2
	> 6	3

\*Grade 0: Normal values for cognition, behavior, neurological examination and ECG  
Grade 1: Anxiety, sleep disorder, easily irritated/excited, tremor, dysgraphia, 5 cps wave  
Grade 2: Narcolepsy, confusion of time, inappropriate behavior, asterixis, ataxia, decreased triphasic wave  
Grade 3: Narcosis, stupor, confusion of sense of space, excessive reflection, contracture, decreased brain wave  
Grade 4: Coma, lack of personality/action, decerebrate rigidity, slow delta wave of 2-3 cps

Total Score	Class	Seriousness
5 - 6	A	Mild
7 - 9	B	Moderate
10 -15	C	Severe

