#### **9.5.2.2.6 Unscheduled Visit**

Subjects can additionally visit separately from a scheduled visit if medical treatment is needed in case of abnormal test result or AE occurs, or follow-up is needed after the occurrence of AE.

Subjects may conduct an unscheduled visit after Visit 2 (Baseline) if examination is required prior to increasing the dose of study drug (from 50 mg/day to 100 mg/day).

If the dose reduction (from 100mg/day to 50mg/day) is required due to events such as AE, the dose may be reduced back to 50mg/day at the discretion of an investigator through

unscheduled site visit or phone visit. In the case of a phone visit, the information such as date of study drug dose change (start date of dose reduction) and relevant Adverse Events shall be collected.

If subjects need to increase the dose back to 100mg/day after the reduction to 50mg/day, they may conduct an unscheduled site visit and the dose may be increased back to 100mg/day at the discretion of an investigator.

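### In the body text, the Child-Pugh dose limits cover only impairment arising after the step to 100 mg/day, so a Class B subject who passes criterion 12 can be enrolled and escalated to twice the protocol's own ceiling

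*Combined protocol and SAP*

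**What the plan says.** **Dose limits.** Section 9.4.1 introduces them with one condition: "If, following the dose increase to 100mg/day, moderate or severe hepatic impairment occurs according to Child-Pugh classification". Under it stand "Moderate hepatic impairment (Child-Pugh B): Do not exceed 50 mg once daily" and, for Class C, termination of study drug. The other dosing texts (synopsis, 9.1.3, 9.4.4, footnote l of Table 3, 9.5.2.2.6) give 50 mg for 14 days and then 100 mg. None of them carries a hepatic condition.

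**Entry.** Criterion 12 in section 9.3.2 excludes "Patients with clinically significant liver function abnormalities defined as > 1.5 times of the upper limit of the normal range of total bilirubin", or ALT or AST above three times the upper limit. It does not mention Child-Pugh class, albumin, ascites, prothrombin time or encephalopathy.

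**Safeguards around the increase.**
- Section 9.1.3: "Subjects who need to increase the dose at the discretion of an investigator shall visit the site (unscheduled) prior to the dose increase".
- Section 9.5.2.2.6: "Subjects may conduct an unscheduled visit after Visit 2 (Baseline) if examination is required prior to increasing the dose of study drug".
- Section 9.3.3: "The investigators may withdraw the subjects from the study at any time for safety or administrative reasons".
- Section 9.1.3, the week-4 rule: "Subjects whose dose cannot be increased to 100 mg/day within 4 weeks following Visit 2 (Baseline) will be dropped out from the clinical trial". Section 9.5.5 lists inability to raise the dose among the reasons for discontinuation.

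Table 3 has no column for the unscheduled visit, and 9.5.2.2.6 lists no examinations for the visit before the increase.

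**The concern.** The protocol sets its own ceiling for Class B but words the trigger so that it reaches only a subject who is already on 100 mg and then becomes impaired. A subject who is Class B at entry is not covered by those words, and the screening criterion is not built to find that subject.

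Such a subject has no consistent route through the trial. Either the dose goes to 100 mg, above the ceiling, or it stays at 50 mg and the subject must leave at week 4. What is at stake is the safety of that subject, and a short exposure to study drug that could not have led to completion within the ceiling.

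**Working it through.** The protocol states no figure on this point to reproduce. The check asks whether a Class B subject can pass criterion 12, and what the plan then prescribes.

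**Inputs.** The Child-Pugh score table and class limits are in 9.4.1 (A 5–6, B 7–9, C 10–15). Criterion 12 is in 9.3.2, the laboratory panel in 9.5.1.3.3, and the visit timing in Table 3. The upper limit of normal (ULN) for bilirubin is not in the documents; I assume 1.0 to 1.3 mg/dL.

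**1. Can a Class B subject pass criterion 12?** Take a subject with normal ALT and AST:

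| Item | Value | Score |
|---|---|---|
| Encephalopathy | none | 1 |
| Ascites | mild | 2 |
| Bilirubin | 1.0 mg/dL | 1 |
| Albumin | 3.0 g/dL | 2 |
| Subtotal | | 6 |

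A prothrombin score of 1, 2 or 3 gives 6 + 1 = 7, 6 + 2 = 8 or 6 + 3 = 9. The subject is Class B whatever the prothrombin result.

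The bilirubin limit in criterion 12 is 1.5 × ULN. For ULN 1.0, 1.2 and 1.3 mg/dL it is 1.5, 1.8 and 1.95 mg/dL. A bilirubin of 1.0 mg/dL is not excluded as long as ULN ≥ 1.0/1.5 = 0.67 mg/dL. So the subject passes.

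**2. Does another criterion catch this subject?** Criterion 6 excludes contraindications to MAO-B inhibitors. Section 9.4.1 calls only Class C contraindicated, so criterion 6 arguably covers Class C at entry but does not clearly reach Class B.

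**3. What dose follows?** The default is 100 mg. Against the Class B ceiling this is 100/50 = 2 times.

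**4. How recent are the liver tests at the increase?** Take Visit 2 as day 0. Visit 1 is between day −21 and day −1, the 50 mg phase is days 1 to 14, and the first 100 mg dose is on day 15. The last scheduled laboratory tests before it are those of Visit 1, so they are 15 + 1 = 16 to 15 + 21 = 36 days old. I give no figure for a later increase. Visit 3 may fall as early as week 8 − 4 = 4; section 9.5.2.2.3 lists laboratory tests there without condition, while Table 3 makes them optional.

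**5. What if the dose is held at 50 mg?** The subject is within the ceiling but cannot reach 100 mg/day, so the week-4 rule requires withdrawal. The same holds for Class B that arises during the 50 mg phase. The text does not say that Class B counts as inability to increase the dose.

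**6. Can the panel give a full score?** No. It includes bilirubin and albumin but not prothrombin time. With albumin 3.0 g/dL and the other three measured items normal, the subtotal is 1 + 1 + 1 + 2 = 5. A prothrombin score of 1 gives 6 (Class A) and a score of 2 gives 7 (Class B).

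**The case against.** **Appendix 1.** It holds the administration instructions for the study drug, the natural place for a hepatic limit, and it was not supplied. A reader might infer that the plan as a whole lacks a limit for Class B at entry. The documents do not support that; only the gap in the body text is shown. The body cites Appendix 1 only for contraindicated and interacting drugs, so 9.4.1 does not send a site there for a hepatic limit.

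**The reading is literal.** An investigator who has just read the 50 mg ceiling is unlikely to escalate a known Class B patient. The wording also has a plausible reason: at 50 mg a Class B subject is already at the ceiling, so a reduction rule is needed only at 100 mg. Both arguments lower the risk. Neither supplies a bar on escalation, and the second does not cover Class C arising on 50 mg.

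**The subject is visible.** History, physical examination and albumin are obtained at Visit 1, and eligibility is reconfirmed and the examination repeated at Visit 2. This stands, and is one reason to expect few cases.

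**Other safeguards.** A reader might infer that nothing beyond the investigator's discretion and the option of safety withdrawal protects this subject. That goes too far: there is also the site visit before a discretionary increase and the mandatory week-4 withdrawal. What remains true is that none of these names a hepatic check, and the week-4 rule acts only once the dose has been held.

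**Frequency.** With bilirubin scoring 1, 45 of the 81 score combinations of the other four items are Class B. A reader might take this as a rate. It counts table cells, not patients.

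**Conclusion.** The point holds as a minor safety matter. In the body text supplied, the trigger in 9.4.1 is narrower than the ceiling it introduces, and criterion 12 does not screen for Child-Pugh class. A subject who is Class B at entry can be enrolled. Followed as written, the schedule takes that subject to twice the ceiling unless the investigator holds the dose, in which case the subject is withdrawn at week 4.

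The documents give no prevalence of hepatic impairment; few subjects are likely to be affected. Endpoints and power are not affected, and nothing here should be read as a criticism of the sample size.

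The conclusion rests on three things: Appendix 1 is unread; the example assumes a bilirubin ULN of at least 0.67 mg/dL; and the words of 9.4.1 are taken to mean impairment that begins after the increase. If Appendix 1 already carries a hepatic limit, the point reduces to making 9.4.1 and 9.3.2 agree with it.

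**What to change.** Check Appendix 1 first. If it has a hepatic limit, word the changes below to agree with it and refer to it in 9.4.1 and 9.3.2.

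1. In 9.4.1, change the trigger to moderate or severe hepatic impairment that *is present or occurs at any time on study drug*. Class B is then never taken above 50 mg, and Class C stops study drug at either dose. State that Class B before escalation counts as inability to reach 100 mg/day, so that the existing week-4 rule applies. Reduction to 50 mg for Class B arising after escalation stays as it is.
2. In 9.3.2 and the synopsis, exclude *known or clinically evident* Child-Pugh B or C impairment, judged from the history, examination, albumin and bilirubin already obtained at Visit 1. Do not require a full score, because prothrombin time is not in the panel.

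The cost is amendment wording and perhaps a very few extra screening failures. The new exclusion loses no Class B subject who could have completed within the 50 mg ceiling, since the week-4 rule would withdraw that subject anyway. No new test is needed, but borderline subjects whose class turns on prothrombin time will not be identified.

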### 9.5.1.3.3 Laboratory Measurements

Laboratory tests to be performed according to the guideline of each site. In case that laboratory test is performed, laboratory abnormality may meet the criteria to qualify as an AE as described in this protocol (see Section 9.5.1.3.1). In these instances, the AE corresponding to the laboratory abnormality will be recorded on the Adverse Event CRF.

Category	Parameters
Hematology	hematocrit, hemoglobin, platelets, RBC count, and WBC count with differential (bands, basophils, eosinophils, lymphocytes, monocytes, neutrophils)
Chemistry	Na, K, Ca, Cl, CPK, BUN, Creatinine, Uric acid, Total bilirubin, Albumin, Total protein, ALT, AST, $\gamma$ -GTP, Alkaline phosphatase
Urinalysis	Specific gravity, pH, Protein, Glucose, Bilirubin, Ketones, RBC, WBC, Creatinine

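### The prothrombin row of the Child-Pugh table in section 9.4.1 does not say what its seconds measure; read as printed, it puts Class A out of reach and moves some subjects from Class B to Class C

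*Combined protocol and SAP*

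**What the plan says.** Section 9.4.1 (Treatment Administered) sets a rule for subjects already raised to 100 mg/day. If "moderate or severe hepatic impairment occurs according to Child-Pugh classification, study drug should be administered as per below guideline". Two consequences follow:

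- "Moderate hepatic impairment (Child-Pugh B): Do not exceed 50 mg once daily"
- "Severe hepatic impairment (Child-Pugh C): Contraindicated (Termination of study drug required" (closing bracket cut from the quote)

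The class comes from a table footnoted to reference 8. It has five items, each scored 1 to 3: encephalopathy, ascites, total bilirubin, albumin and prothrombin time. The prothrombin row is labelled "Prothrombin Time (seconds" (closing bracket cut) and its cut-points are < 4 = 1, 4 - 6 = 2 and > 6 = 3. Neither the row nor the notes under the table mention a control value or a prolongation. A second table turns the total into a class: 5 to 6 is A (mild), 7 to 9 is B (moderate) and 10 to 15 is C (severe).

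Section 9.5.1.3.3 lists the laboratory panel:

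- Hematology covers "hematocrit, hemoglobin, platelets, RBC count, and WBC count with differential".
- Chemistry includes "Na, K, Ca, Cl, CPK, BUN, Creatinine, Uric acid, Total bilirubin, Albumin, Total protein, ALT, AST", which supplies two of the Child-Pugh items, bilirubin and albumin.
- Urinalysis is "Specific gravity, pH, Protein, Glucose, Bilirubin, Ketones, RBC, WBC, Creatinine".

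No coagulation test appears there, in Table 3 or in the visit lists of section 9.5.2.2.

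**The concern.** The bilirubin and albumin rows of the same table are absolute values with units. A reader who treats the prothrombin row in the same way will enter the measured time in seconds. If ordinary times lie above 6 s, that row gives every such subject its highest score, whatever the state of the liver.

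The table is operative text. The class it returns sets a dose limit or ends study drug, so two extra points can change a subject's treatment. The rule is applied at about 20 sites (section 6). If some sites read the row literally and others silently reinterpret it, the same findings could lead to different classes and different actions.

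**Working it through.** **Inputs from section 9.4.1.** Five items scored 1 to 3; prothrombin cut-points < 4, 4 - 6 and > 6; classes A 5-6, B 7-9 and C 10-15.

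**Assumption, not in the documents.** An ordinary prothrombin time is above 6 s. The range 9 to 15 s is used for illustration.

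**Step 1: reproduce the printed range.** The minimum is 5 × 1 = 5 and the maximum is 5 × 3 = 15. This matches the class table, which runs from 5 to 15, so the items and classes fit together in principle.

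**Step 2: apply the row as printed.** Every value from 9 to 15 s exceeds 6, so the prothrombin score is 3. The result does not depend on where in that range the value falls. The lowest possible total is 4 × 1 + 3 = 7, which is Class B. Class A needs a total of 6 or less and hence a prothrombin score of 1 or 2, that is, a printed value of 6 s or less.

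**Step 3: see where the class changes.** Let S be the sum of the other four items (4 to 12). The total is S plus the prothrombin score.

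| S | score 1 | score 2 | score 3 |
|---|---|---|---|
| 4 | 5 (A) | 6 (A) | 7 (B) |
| 5 | 6 (A) | 7 (B) | 8 (B) |
| 6 | 7 (B) | 8 (B) | 9 (B) |
| 7 | 8 (B) | 9 (B) | 10 (C) |
| 8 | 9 (B) | 10 (C) | 11 (C) |
| 9 to 12 | 10 to 13 (C) | 11 to 14 (C) | 12 to 15 (C) |

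Scoring 3 instead of 1 changes the class at S = 4 and 5 (A to B) and at S = 7 and 8 (B to C). It makes no difference at S = 6 or at S = 9 and above.

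**Step 4: count combinations.** The other four items have 3^4 = 81 score combinations. The numbers giving S = 4, 5, 7 and 8 are 1, 4, 16 and 19, and 1 + 4 + 16 + 19 = 40. So the prothrombin score can change the class in 40 of 81 combinations. With that score fixed at 3, none of the 81 is Class A, 15 are Class B and 66 are Class C. These count table cells with equal weight; they are not probabilities for patients.

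**Step 5: test sensitivity to the reading.** Suppose instead that the seconds were an excess over a control value, with controls of 10 to 14 s (again an assumption). For prothrombin times of 11 to 13 s the excess runs from 11 − 14 = −3 to 13 − 10 = 3. All of these are below 4, so the score is 1. With the other items at their minimum the total is 4 + 1 = 5, Class A. The outcome therefore turns on a definition that the row does not give.

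**The case against.** The strongest objection is that few subjects are exposed. The rule starts only if hepatic impairment arises after the increase to 100 mg/day, and no visit list requires Child-Pugh scoring of everyone. Exclusion criterion 12 already removes clinically significant bilirubin, ALT or AST elevations at entry. A subject normal on the other four items has little reason to be scored at all. All of this stands, and it limits the size of the problem.

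An experienced reader may also supply a prolongation reading, and the column heading (abnormal value or degree) leaves room for one. But that heading covers every row, including those in absolute units, and no text states the reading. Reference 8 and Appendix 1 were not available. The table is split across a page in the extracted text, so a lost qualifier cannot be wholly excluded, although the row's cut-points and scores look complete.

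A reader might go further and infer that the rule cannot be operated, because prothrombin time is missing from the panel. The documents do not support that. Section 9.5.1.3.3 says "Laboratory tests to be performed according to the guideline of each site", section 9.5.2.2.6 allows unscheduled visits for an abnormal result or an adverse event, and section 9.5.1.3.1 contemplates laboratory measurements beyond those the protocol requires. An event-driven rule may use an event-driven test. The missing panel entry is a detail to clarify and does not block the rule.

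**Conclusion.** The point holds for the row. As printed, and on the assumption that ordinary prothrombin times exceed 6 s, Class A cannot be reached and the lowest class is B. Subjects whose other items total 7 or 8 fall in Class C, where a prothrombin score of 1 would put them in Class B. Nothing in the documents supplies a reading that repairs this. Because the row feeds a dose and termination rule, it deserves correction although few subjects are likely to be affected; the documents give no expected number.

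Two larger inferences should be resisted:

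- **Drop-out.** The row does not by itself send an otherwise normal subject to termination. That subject reaches 7, Class B, and Class C requires the other four items to total at least 7. The four-week withdrawal rule in section 9.1.3 concerns failure to reach 100 mg/day, whereas this rule applies after that dose has been reached.
- **Trial results.** The sample size and the efficacy analyses do not use the Child-Pugh score and are not affected.

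**What to change.** Reconcile the prothrombin row of section 9.4.1 with its cited source (reference 8), and state in the row what quantity the seconds measure, so that the item scores and the class table agree. As a minor clarification, add a sentence saying that prothrombin time is not part of the section 9.5.1.3.3 panel and would be obtained when the rule is applied.

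The cost is one row label and one cross-reference. No new visit, routine test or analysis is needed. Which dose or stopping rule should apply in each class is outside this point, and none is proposed.
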